4.2. Study Design Rationale

Pomalidomide + Dex has shown activity in several phase 1, phase 2 trials, and most recently in a randomized, phase 3 trial. The dose of 4 mg was established in a Phase 1 trial (CC-4047-MM-002, NCT00833833) which also achieved 42% minimal response or better, 21% partial response or better and 3% complete response in a heavily pretreated population (Richardson, 2013). In a Phase 2 trial following this Phase 1, response rates of at least PR of 34% were achieved as well as a median PFS of 4.6 months (Richardson, 2011a). A Phase 2 trial conducted by the IFM confirmed high efficacy of the combination of POM and Dex in subjects refractory to BTZ and LEN with response rates of 35% (Leleu, 2013). Recently, results of a Phase 3 trial comparing POM + Dex to high-dose Dex in subjects refractory and heavily pretreated patients, including LEN and BTZ pretreatment, have shown significant improvement in PFS as well as OS (Dimopoulos, 2012).

The present study is a multicenter, open-label, phase 2 study in the United States and Canada designed to further evaluate the efficacy and safety of combination POM + LD-Dex or POM+DARA+LD-Dex in the US, Canada and Japan in subjects with relapsed MM or refractory MM who received LEN-based therapy in the first or second line. Pomalidomide is efficacious in pretreated patients, especially those patients who are not only refractory to BTZ but also LEN and has shown statistically significant improvement in PFS. In a later line setting, the current treatment options are limited. Pomalidomide provides treatment control after LEN and BTZ, where there is still a high unmet medical need. The clinical efficacy of Pomalidomide in advanced relapsed and refractory MM does not appear to be affected by prior refractory disease status (Richardson, 2013). In the MM-002 clinical trial, response rates (25%-30%) and overall survival (OS; median 13.4-14.4 months) were similar for patients refractory to LEN, BTZ, LEN + BTZ, and the overall patient population. Similarly, the Mayo Clinic trial has demonstrated response rates between 32% to 38% in patients refractory to LEN and 26% to 29% in patients refractory to LEN + BTZ (Lacy, 2009). In the Japanese phase 2, MM-011 clinical trial, response rates (33% - 43%) were similar for patients' refractory to LEN and LEN+BTZ and the overall patient population (Ichinohe, 2016). Additionally, in the phase 3 MM-003 clinical trial, POM + Dex treatment of dual refractory patients (LEN and BTZ) significantly improved PFS (3.2 months, $P < 0.001$; HR = 0.48) and OS (not reached, $P < 0.001$; HR = 0.53) compared with those treated with HiDex; 1.7 and 7.4 months, respectively). These phase 3 data met the primary PFS endpoint and crossed the upper boundary for superiority of OS (Dimopoulos, 2012).

Daratumumab is a human anti-CD38 IgG1K monoclonal antibody with remarkable safety and activity as monotherapy in heavily treated relapsed and refractory multiple myeloma (MM) (Lokhorst, 2014; Lonial, 2016). In the GEN 501 clinical trial, response rates (36% - 44%) were similar in patients LEN, BTZ, LEN+BTZ and the overall patient population (Lokhorst, 2015; Iida, 2017). Daratumumab has demonstrated clinical activity in combination with LEN and Dex in relapsed or refractory MM and in Japanese subjects (Plesner, 2014; Dimopoulos, 2016; Suzuki, 2018). Daratumumab has also show clinical benefit in combination with BTZ and Dex in relapsed and/or refractory MM (Palumbo, 2016).

Recently an open label multi-center phase 1b clinical trial assessed the combination of POM+DARA+Dex in 103 patients with relapsed or refractory multiple myeloma. The combination demonstrated an ORR of

68% in a heavily pretreated patient population (median 4 prior lines of therapy) and ORR of 58% in double refractory (PI and IMiD). The toxicity profile of the three-drug combination was also well tolerated with most common Grade 3 toxicities being hematologic in nature including neutropenia (78%), anemia (28%), leukopenia (24%) and thrombocytopenia (19%) (Chari, 2017).

There have been no clinical trials evaluating the efficacy and safety of LEN following treatment with Pomalidomide. Preclinical data in mice suggest that Pomalidomide retains its antimyeloma activity in LEN-refractory disease to a much greater extent than LEN does in Pomalidomide-refractory disease. Investigators at the Mayo Clinic have reported outcomes for patients who relapsed after treatment with Pomalidomide. Only 7 out of 52 (13%) patients received LEN-based therapy as first salvage, and 2 out of 7 (29%) achieved a partial response or better; 5 out of 7 (71%) had SD or PD (Lacy, 2009).

Data support the idea that Pomalidomide provides consistent outcomes regardless of exposure to prior therapy. Results from the IFM 2009-02, MM-002, and Mayo Clinic trials demonstrated consistent responses across all subgroups (eg, LEN-refractory, BTZ refractory, and LEN/BTZ dual-refractory \pm prior stem cell transplantation). Additionally, preclinical data in mice suggest that POM + Dex overcomes acquired resistance to LEN + Dex. Taken together, these results suggest minimal cross resistance for POM following LEN.

All-trans retinoic acid (ATRA) has been shown in both cell lines and primary MM samples to increase CD38 expression levels and also to reduce expression of the complement-inhibitory proteins CD55 and CD59 (Nijhof et al, 2015). This resulted in significant enhancement of activity of Daratumumab in vitro and in humanized MM mouse models. Daratumumab and ATRA exhibit a strong synergy in MM cells derived from Dara-naïve patients and from patients with Dara-refractory disease, providing preclinical rationale for further evaluation of Daratumumab combined with ATRA in MM patients. Preliminary data from phase 1 trials combining Daratumumab and ATRA have shown that the combination is safe using ATRA 45 mg/m²/day dose.

Second primary malignancies will be monitored as events of interest and will be reported as a serious adverse event (SAE) regardless of causal relationship to investigational product (IP). The multicenter nature as well as the inclusion of patients in Japan of the study provides reassurance that the results are likely to have general applicability and the size of the study allows accurate description of the nature, frequency, and severity of the AE profile. Subjects will receive study treatment until PD or discontinuation. In studies evaluating agents for subjects with refractory MM or relapsed and refractory progressing or relapsed malignant diseases, it is common practice to continue study treatment until PD or intolerable toxicity develops. All subjects will be followed for OS, subsequent anti-myeloma therapies and SPMs.

4.3. Study Duration

This study will consist of the following consecutive phases: Screening, Treatment and Follow-up.

The study will remain open to enrollment until the target subject enrollment of approximately 42 subjects has been reached. Given our current patient population we expect to complete enrollment in two years.

Each subject will be followed for up to 12 months after enrollment (unless the follow-up is shorter due to withdrawal of consent, loss to follow-up, or death).

4.4. End of Trial

The End of Trial is defined as either the date of the last visit of the last subject to complete the study, or the date of receipt of the last data point from the last subject that is required for primary, secondary and/or exploratory analysis, as pre-specified in the protocol and/or the Statistical Analysis Plan, whichever is the later date.

5. PROCEDURES

5.1. Study Entry

Prior to screening, subjects must sign an informed consent document. All screening assessments must be completed within 28 days prior to start of Cycle 1, with the exception of the skeletal survey, which may be performed within 60 days prior to initiation of study treatment.

Confirmation of diagnosis (including date of confirmed initial diagnosis and, if available, myeloma stage at time of initial diagnosis per the Salmon-Durie Criteria and/or the International Staging System, medical history, prior cancer and surgical history, and review of prior medications should be documented during the screening period. All prior radiotherapy, surgeries, and anti-myeloma therapies must be recorded in the electronic case report form (eCRF), including approximate dates for each therapy and the date of progression for each regimen. Results for any local cytogenetic testing (prefer fluorescence in situ hybridization [FISH] results), if available, as part of medical history, will be collected in the eCRF. See Table 1 (Table of Events) for a complete list of the required assessments during screening.

If the subject's safety and efficacy laboratory assessments performed at screening are within 7 days of enrollment into the study, they do not need to be repeated at Cycle 1 Day 1 and can be used as baseline results. The start of study drug dosing is designated as Cycle 1 Day 1. A 14-day wash-out period is required for any prior anti-myeloma therapy before study treatment is initiated.

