Dexamethasone will be administered at 40 mg once weekly on days 1,8,15 for patients 75 years old and younger and at 20 mg once weekly on days 1,8,15 for patients older than 75. Patients may stay on their currently administered steroid regimen if it does not match the above.

ATRA will be administered in a divided dose of twice daily as an oral formulation at 35.5 mg/m²/day for the phase 1b portion, then escalated to 45mg/m²/day for 3 days. The first administration of ATRA will be given in the morning, two days before the scheduled Dara infusion. The last administration of ATRA will

be given in the evening of the day that Dara was administered (days -2, -1, and 0; day 0 is the day of Dara infusion).

Treatment repeats every 28 days for at least 8 cycles in the absence of disease progression or unacceptable toxicity. Patients achieving stable disease may continue to receive treatment in the absence of disease progression or unacceptable toxicity.

After completion of the study treatment, patients are followed up at 28 days and then every 3 months for up to 12 months. Subjects will be evaluated for disease response during each cycle and at the end of study.

Adverse events (secondary endpoint) will be recorded and graded according to the National Cancer Institute Common Terminology Criteria for Adverse Events (NCI-CTCAE) (Version 5).

Tumor response, based on the investigator's assessment, will be evaluated according to the International Myeloma Working Group (IMWG) response criteria (Durie, 2006) and will be modified (mIMWG) to add criteria for MR (Kyle, 2009) (per Appendix B).

The phase 1b portion will estimate the maximum tolerated dose (MTD) by a standard 3+3 design using data collected in the dose escalation phase. MTD will be defined for each dosing level. A maximum of 2 dose levels are planned (35.5 mg/m²/day to 45 mg/m²/day). For phase 1b the maximum number of evaluable patients is planned to be 12.

The phase 2 portion will evaluate the clinical activity of Dara + Pom + Dex + ATRA. A Simon's two-stage minimax design will be used.

Analysis of biomarkers will also be explored in subjects who consent to participate in the exploratory biomarker study.

All subjects will be maintained on the Pomalidomide pregnancy prevention program (Appendix D) for the duration of the study.

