For all subjects who enroll into this study, study visits and serial measurements of safety and efficacy will be performed as outlined in Table 1, Table of Events. The overall study design is depicted in Figure 1.

[figure not shown]

Figure 1: Overall study design

Table 1: Table of events

	SCREENING	CYCLE 1					CYCLE 2+					END OF TREATMENT	FOLLOW UP
PROCEDURE	Day -28 to -1	Days -2, -1 (+/- 10 days)	Day 1 (+/- 10 days)	Day 8 (+/- 10 days)	Day 15 (+/- 10 days)	Day 22 (+/- 10 days)	Days -2, -1 (+/- 10 days)	Day 1 (+/- 10 days)	Day 8 (+/- 10 days)	Day 15 (+/- 10 days)	Day 22 (+/- 10 days)	28 days after last dose (+/- 28 days)	Q3 Months (+/- 28 days)
Informed Consent	X												
Inclusion/Exclusion Criteria	X												
Medical/Treatment History	X												
Vital Signs ^h	X	X	X	X	X		X	X	X	X	X	X	
Physical Exam	X	X	X	X	X		X	X	X	X	X	X	
Neurologic Exam	X		X					X					
Weight	X		X					X				X	
ECOG	X												
Patient reported outcomes – Quality of Life (QoL)	X		X					X				X	
PFT/FEV1 testing for patients with history of COPD/persistent asthma	X												
AE/SAE review		Continuous											
Medication evaluation	X	Continuous											
LOCAL LABS													
Venipuncture (Facility Fee)	X												
CBC (w/ platelet count)	X	X	X	X	X	X	X	X	X	X	X	X	
Serum Chemistry	X	X	X	X	X	X	X	X		X		X	
Hepatitis B (HBV) serology ^e	X												
HBV DNA testing ^f	X	Q12W during treatment, at the End of Treatment Visit, and Q12W for up to 6 months after the last dose of study treatment											
TSH, T3, Free T4, Coagulation	X												

	SCREENING	CYCLE 1					CYCLE 2+					END OF TREATMENT	FOLLOW UP
PROCEDURE	Day -28 to -1	Days -2, -1 (+/- 10 days)	Day 1 (+/- 10 days)	Day 8 (+/- 10 days)	Day 15 (+/- 10 days)	Day 22 (+/- 10 days)	Days -2, -1 (+/- 10 days)	Day 1 (+/- 10 days)	Day 8 (+/- 10 days)	Day 15 (+/- 10 days)	Day 22 (+/- 10 days)	28 days after last dose (+/- 28 days)	Q3 Months (+/- 28 days)
Thiamine testing	X		X					X					
Urinalysis	X												
Pregnancy Test	X		X					X					
Triglycerides	X		X	X	X	X		X	X	X	X		X
SPEP, UPEP, Serum/Urine Immunofix., Quant IgGs, 24Hr Urine, SFLC, B2 Micro	SOC		X					X					
CORRELATIVE SAMPLING													
Correlative Studies – peripheral blood collection, stool samples	X ^{b,d}	X ^{b,d}	X ^{b,d}					X ^{c,d}				X ^{c,d}	X ^{c,d}
Correlative Studies – bone marrow	X ^b	X ^b	X ^b									X	X ^c
CARDIOLOGY, PATHOLOGY, RADIOLOGY													
12-lead ECG	X ^g	X		X	X	X	X						
ECHO	X												

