Bone Marrow Biopsy/Aspirate & Interp	SOC							X					X ⁱ
Radiological Assessments	SOC												
TREATMENT													
ATRA study drug (PO)		X	X				X	X					
Pomalidomide study drug (PO)		Pomalidomide will be administered on days 1-21 of cycle											
Dexamethasone study drug	X		X	X	X			X	X	X			
Dexamethasone Admin (IV)			X	X	X			X	X	X			
Daratumumab study drug	X		X ^a	X ^a	X ^a	X ^a		X ^a	X ^a	X ^a	X ^a		

	SCREENING	CYCLE 1					CYCLE 2+					END OF TREATMENT	FOLLOW UP
PROCEDURE	Day -28 to -1	Days -2, -1 (+/- 10 days)	Day 1 (+/- 10 days)	Day 8 (+/- 10 days)	Day 15 (+/- 10 days)	Day 22 (+/- 10 days)	Days -2, -1 (+/- 10 days)	Day 1 (+/- 10 days)	Day 8 (+/- 10 days)	Day 15 (+/- 10 days)	Day 22 (+/- 10 days)	28 days after last dose (+/- 28 days)	Q3 Months (+/- 28 days)
Daratumumab Admin (SC)			X ^a	X ^a	X ^a	X ^a		X ^a	X ^a	X ^a	X ^a		

^a During 28-day treatment cycles, patients will receive Dara 1800 mg subcutaneous (SC) at their current dose upon enrollment onto the study depending on their cycle. They will receive Dara depending on the cycle they are in. If they are on cycles 1-2 then they will receive Dara 1800 mg SC on days 1,8,15,22; if they are on cycles 3-6 they will receive Dara 1800 mg SC on days 1 and 15; and if they are on cycle 7 or beyond they will receive Dara 1800 mg SC on day 1.

^b Baseline correlative studies may be collected at screening, day -2/-1 or cycle 1 day 1.

^c After baseline sample, correlative studies for peripheral blood and stool will be collected at cycle 2 day 1, end of treatment, and at time of relapse.

^d Any time patients receive antibiotics while on study they should have stool and peripheral blood collected before starting antibiotics and upon completion of antibiotics (within a 7 day window). Patients should be provided with multiple stool kits prior to study so that they may collect stool even if antibiotics are prescribed by an outside physician.

^e Local testing for hepatitis B surface antigen (HBsAg), hepatitis B surface antibody (Anti-HBs), and hepatitis B core antibody (Anti-HBc). Refer to Section 5.3.

^f For subjects with serologic evidence of resolved HBV infection (i.e., positive Anti-HBs or positive Anti-HBc) at Screening, HBV DNA testing by PCR must be performed locally. Refer to Section 5.4.

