6.2. Inclusion criteria

Subjects must satisfy the following criteria to be enrolled in the study:

1. Documented multiple myeloma with prior exposure to an IMiD, PI, and CD-38 moAb.
2. Patients must have 2 or more prior lines of therapy.
3. Patients must have been previously exposed to:
 - a. Dara+Len+Dex and must have achieved at least stable disease to this combination.
or;
 - b. Dara + Pom + Dex and must have achieved at least stable disease to this combination.
4. Histologically confirmed and relapsed multiple myeloma with measurable disease, defined by at least one of the following:
 - a. Serum monoclonal protein ≥ 0.5 g/dL;
 - b. Monoclonal protein in the urine on 24-hour electrophoresis ≥ 200 mg;
 - c. Serum immunoglobulin free light chain (FLC) ≥ 10 mg/dL (100 mg/L) provided serum FLC ratio is abnormal;
 - d. New or progressing biopsy proven plasmacytoma on exam or imaging; or
 - e. Bone marrow plasma cells $\geq 20\%$;
5. Cycle 1 day 1 of study treatment must be within 3 months of last exposure to Daratumumab.
6. Life expectancy >3 months

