Note: If the childbearing potential changes after start of the study (e.g., woman who is not heterosexually active becomes active, premenarchal woman experiences menarche)

- a woman must begin a highly effective method of birth control, as described above.

11. A woman of childbearing potential must have 2 negative serum (β human chorionic gonadotropin) or urine pregnancy tests during screening, the first one within 28 days prior to the first dose of study drug and the second within 24 hours prior to the first dose of study drug.

12. A man who is sexually active with a woman of childbearing potential and has not had a vasectomy must agree to use a barrier method of birth control e.g., either condom with spermicidal foam/gel/film/cream/suppository or partner with occlusive cap (diaphragm or cervical/vault caps) with spermicidal foam/gel/film/cream/suppository, and all men must also not donate sperm during the study and for 3 months after receiving the last dose of study drug.

13. Subjects must be willing and able to adhere to the prohibitions and restrictions specified in this protocol and referenced in the informed consent form (ICF).

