2.4. Pregnancy Testing

Medically supervised pregnancy tests with a minimum sensitivity of 25 mIU/mL must be performed for FCBP.

Females of childbearing potential must have two negative pregnancy tests (sensitivity of at least 25 mIU/mL) prior to starting pomalidomide. The first pregnancy test must be performed within 10 to 14 days prior to the start of pomalidomide and the second pregnancy test must be performed within 24 hours prior to the start of pomalidomide. The subject may not receive pomalidomide until the study doctor has verified that the results of these pregnancy tests are negative.

Females of childbearing potential with regular or no menstrual cycles must agree to have pregnancy tests weekly for the first 28 days of study participation and then every 28 days while taking pomalidomide, at study discontinuation, and at Day 28 following the last dose of pomalidomide.

Females of childbearing potential with irregular menstrual cycles must agree to have pregnancy tests weekly for the first 28 days of study participation and then every 14 days while taking pomalidomide, at study discontinuation, and at Days 14 and 28 following the last dose of pomalidomide.

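### Section 5.1 starts study drug dosing on Cycle 1 Day 1 although ATRA starts on Day -2, so the timing of the second pregnancy test is ambiguous; and no pregnancy stop rule names ATRA

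*Combined protocol and SAP*

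**What the plan says.** **Timing of the test**

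- Section 6.2 opens with "Subjects must satisfy the following criteria to be enrolled in the study". Inclusion criterion 11 then asks women of childbearing potential for two negative tests during screening, the first within 28 days and "the second within 24 hours prior to the first dose of study drug". The Protocol Summary repeats the criterion.
- Section 5.1: "The start of study drug dosing is designated as Cycle 1 Day 1". The same section wants all screening assessments finished before Cycle 1 starts.
- Section 4.1: "The first administration of ATRA will be given in the morning, two days before the scheduled Dara infusion". ATRA is taken twice daily for three days, ending on the evening of the daratumumab day. Section 7.5 calls that day Day 1.
- Table 1 has a row whose label begins "ATRA study drug (PO", marked in the Days -2/-1 column and on Day 1. Its "Pregnancy Test" row is marked at screening and on Day 1 of each cycle, and is blank at Days -2/-1. The screening column runs to Day -1.
- Section 4.1 also says: "All subjects will be maintained on the Pomalidomide pregnancy prevention program". That plan (Appendix C, 2.4) states: "The first pregnancy test must be performed within 10 to 14 days prior to the start of pomalidomide". It places the second test in the 24 hours before pomalidomide, which starts on Day 1.

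**Stopping for pregnancy**

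- Section 10.9.1 stops the investigational product at once for a pregnancy or suspected pregnancy.
- Section 7.1 describes daratumumab as the only investigational product supplied. Section 10.3.1 lists the products as pomalidomide, daratumumab and dexamethasone.
- Appendix C, 2.5.2.1 stops pomalidomide on a positive test and holds it during a missed-period work-up.
- Section 7.6, on discontinuing ATRA, does not mention pregnancy.

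**The concern.** Criterion 11 is meant to give a negative test no more than 24 hours old when study drug begins. ATRA is the drug this trial adds, and it is the first one taken. If a site takes Section 5.1 at its word, the 24-hour test is tied to Day 1 and a pregnancy it detects is found after ATRA has been given.

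Pregnancy is exclusion criterion 7, so such a woman would be found ineligible after dosing. She would already belong to the safety population of Section 9.4, which needs only one dose. In phase 1b she would be replaced under Section 7.4 if she missed a Cycle 1 ATRA dose.

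The stop rule raises a second, smaller problem. A site that reads Section 10.9.1 literally finds an instruction for the other three drugs and none for ATRA.

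**Working it through.** The plan gives no figure of its own to reproduce. The check is a count of doses and days.

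**Inputs.** Let D be the daratumumab day (Day 1).

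- ATRA days: D-2, D-1 and D, twice daily (Sections 4.1 and 7.5).
- First ATRA dose: morning of D-2 (Section 4.1).
- Pomalidomide starts on D (Table 1). Its time of day is not given.
- First Appendix C test: D-14 to D-10.

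**Doses.** Total in Cycle 1: 3 days × 2 = 6. Taken before D: 2 days × 2 = 4.

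**Reading A: criterion 11 with Table 1's ATRA label.** The test falls within 24 hours before the D-2 morning dose. ATRA doses before it: 0 of 6. The last required negative test is at most 24 hours old at the first ATRA dose.

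**Reading B: Section 5.1, Table 1's test row and Appendix C.** The test falls within 24 hours before the anchor dose on D. The count depends on when that dose is taken, which is an assumption here:

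| Anchor dose on D taken | Test at the 24-hour limit follows | Test just before the anchor dose follows |
|---|---|---|
| no later than the morning ATRA dose | 2 doses | 4 doses |
| after the morning and no later than the evening ATRA dose | 3 | 5 |
| after the evening ATRA dose | 4 | 6 |

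In the first row, with the anchor and the morning ATRA dose taken together, the test comes 24 to 48 hours after the first ATRA dose.

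Table 1's screening column closes on Day -1, so a test on D cannot be criterion 11's screening test. With a morning anchor, a Day -1 test follows 2 doses if done just before that morning's ATRA and 3 if done between the two doses. It reaches 4 only if done after the evening dose.

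**Age of the last required negative test under Reading B.** Appendix C's first test precedes the first ATRA dose by 14 - 2 = 12 days at most and 10 - 2 = 8 days at least. That compares with at most 24 hours under Reading A.

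**Stop rules side by side**

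| Section | What stops | ATRA named? |
|---|---|---|
| 10.9.1 with 7.1 | daratumumab | no |
| 10.9.1 with 10.3.1 | pomalidomide, daratumumab, dexamethasone | no |
| Appendix C, 2.5.2.1 | pomalidomide | no |
| 7.6 | ATRA, but for toxicity or delay | pregnancy not listed |

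Daratumumab stops on either definition, and ATRA days are set from the daratumumab day, so later ATRA courses lapse with it. A course already under way is different. After a positive test on D before dosing, 6 - 4 = 2 ATRA doses remain, and no rule expressly covers them.

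**The case against.** The strongest reply is that the eligibility text already gives the right answer. Criterion 11 is a condition of enrolment, it places both tests in screening, and Table 1 calls ATRA a study drug. Section 5.1 wants screening done before Cycle 1 starts, Table 1 puts Days -2/-1 under Cycle 1, and Section 7.4 speaks of Cycle 1 doses of ATRA. The Section 5.1 sentence about Day 1 sits among baseline laboratory and washout rules, and Appendix C's test can simply be an additional one. All of this stands: the late test is open to a site but not required of it. The ambiguity nevertheless remains, because Section 5.1 expressly defines when study drug dosing starts and the schedule marks no test at Days -2/-1.

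The reply on the stop rule is that ATRA would in practice end with daratumumab, and that Section 10.9.1 covers suspected pregnancy. That also stands, apart from the doses left in a course already begun.

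A reader might infer more than the documents support:

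- *ATRA may be given with no prior pregnancy test.* No. An earlier negative test is always required; only the second test is in question. Contraception under criterion 10, and under Appendix C from 28 days before pomalidomide, already covers Day -2.
- *The plan exposes a fetus to a stated ATRA hazard.* The documents state no fetal risk for ATRA. Section 1.4 mentions effects on embryonic cells and goes no further.
- *Exactly 2 to 4 doses precede the test.* That range needs morning dosing on Day 1.
- *ATRA would continue through a pregnancy.* Nothing provides for ATRA without daratumumab.

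**Conclusion.** The plan contains two incompatible starting points for study drug, and the second pregnancy test depends on which one a site uses. On one reading it precedes every ATRA dose. On the other it may follow about 2 or more of the 6 Cycle 1 doses, with the last required negative test 8 to 12 days old when ATRA begins. The dose count rests on assumed clock times; the test age rests on Appendix C's schedule being followed.

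The absence of ATRA from every pregnancy stop rule is a literal gap with limited practical effect.

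The severity is minor. Only women of childbearing potential are concerned, the documents do not give their number, and no efficacy endpoint is affected. The point rests on criterion 11 and exclusion 7 and does not depend on any claim about ATRA's effect on a fetus.

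**What to change.** 1. In criterion 11 (Section 6.2 and its Protocol Summary copy) and in Section 5.1, state that for pregnancy testing the first dose of study drug is the first ATRA dose, on Day -2. Mark this test in Table 1. Keep Appendix C's test before pomalidomide. Leave the 14-day washout (Section 5.1 and exclusion 16) and the Section 8.2 prohibition as they are, so that neither window moves.
2. In Section 10.9.1, and in Section 7.6, name ATRA among the drugs discontinued immediately for pregnancy, a positive test or suspected pregnancy.

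The cost is wording in these sections and one Table 1 row, plus one re-timed or added urine or serum test for the women concerned. That test falls on Day -3 or early on Day -2, with the result needed before a morning oral dose. Table 1 marks blood counts and chemistry in a combined Days -2/-1 column, which does not establish a pre-dose visit on Day -2, so a separate sample or visit may be needed. With Appendix C's two tests kept, a woman may have three baseline tests.
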